5.4.6 Debriefing

NA

5.5 Informed consent will not be obtained – request to completely waive the informed consent requirement

5.5.1 Indicate why the research could not practicably be carried out without the waiver of consent

NA

5.5.2 Describe why the research involves no more than minimal risk to subjects.

NA

5.5.3 Describe why the alteration/omission will not adversely affect the rights and welfare of subjects.

NA

5.5.4 If the research involves using identifiable private information or identifiable biospecimens, describe why the research could not be practicably be carried out without using such information or biospecimens in an identifiable format.

NA

5.5.5 Additional pertinent information after participation

NA

5.6 Consent – Other Considerations

5.6.1 Non-English-Speaking Subjects

NA

5.6.2 Cognitively Impaired Adults

5.6.2.1 Capability of Providing Consent

NA

5.6.2.2 Adults Unable to Consent

NA

5.6.2.3 Assent of Adults Unable to Consent

NA

5.6.3 Subjects who are not yet adults (infants, children, teenagers)

5.6.3.1 Parental Permission

For all subjects under the age of 18, parental/legal guardian permission will be obtained using an informed consent form. The consent process will be documented in the subject's research records and a copy of the signed ICF will be provided.

5.6.3.2 Assent of subjects who are not yet adults

The Information Sheet will be provided to all potential participants ages 12-17. They will be given ample time to review the document in a private room. All questions will be answered by study team members prior to providing assent.

Assent will be obtained and documented for all children participants in this study, as subjects will be at least 12 years of age. Assent will be documented in the ICF and in the subject's research chart.

6.0 HIPAA Research Authorization and/or Waiver or Alteration of Authorization

6.1 Authorization and/or Waiver or Alteration of Authorization for the Uses and Disclosures of PHI

Check all that apply:

- ☐ **Not applicable, no identifiable protected health information (PHI) is accessed, used or disclosed in this study.** *[Mark all parts of sections 6.2 and 6.3 as not applicable]*
- ☒ **Authorization will be obtained and documented as part of the consent process.** *[If this is the only box checked, mark sections 6.2 and 6.3 as not applicable]*
- ☒ **Partial waiver is requested for recruitment purposes only (Check this box if patients' medical records will be accessed to determine eligibility before consent/authorization has been obtained).** *[Complete all parts of sections 6.2 and 6.3]*
- ☐ **Full waiver is requested for entire research study (e.g., medical record review studies).** *[Complete all parts of sections 6.2 and 6.3]*
- ☐ **Alteration is requested to waive requirement for written documentation of authorization (verbal authorization will be obtained).** *[Complete all parts of sections 6.2 and 6.3]*

6.2 Waiver or Alteration of Authorization for the Uses and Disclosures of PHI

6.2.1 Access, use or disclosure of PHI representing no more than a minimal risk to the privacy of the individual

6.2.1.1 Plan to protect PHI from improper use or disclosure

Information is included in the “Confidentiality, Privacy and Data Management” section of this protocol.

6.2.1.2 Plan to destroy identifiers or a justification for retaining identifiers

All study materials that have identifiable information will be kept until notified by the sponsor. If a subject has a phone screen conducted and does not schedule an appointment or if they do not want their information kept for future studies the phone screening is shredded.

6.2.2 Explanation for why the research could not practicably be conducted without access to and use of PHI

Research needs to use PHI to ensure subject meets eligibility criteria.

6.2.3 Explanation for why the research could not practicably be conducted without the waiver or alteration of authorization

Participants are screened prior to scheduling them for their research appointment to help determine if the patient is potentially eligible for the study. This helps sift through candidates for appointments so patient’s time is not wasted.

6.3 Waiver or alteration of authorization statements of agreement

Protected health information obtained as part of this research will not be reused or disclosed to any other person or entity, except as required by law, for authorized oversight of the research study, or for other permitted uses and disclosures according to federal regulations.

The research team will collect only information essential to the study and in accord with the ‘Minimum Necessary’ standard (information reasonably necessary to accomplish the objectives of the research) per federal regulations.

Access to the information will be limited, to the greatest extent possible, within the research team. All disclosures or releases of identifiable information granted under this waiver will be accounted for and documented.

7.0 Study Design and Procedures

7.1 Study Design

This is a prospective interventional study of topical ruxolitinib 1.5% cream twice a day for the treatment of early stage (stage I and II) HS.

7.2 Study Procedures**7.2.1 Screening visit**

Informed consent	Laboratory screening obtained* 
 • Hepatitis B and Hepatitis C surface and core antibodies • Interferon-releasing assay for tuberculosis (or chest x-ray for those with a history of positive PPD) • Complete blood count (CBC) with differential • Hepatic panel (AST, ALT, Alk phos) • Fasting lipid panel (total, high-density, and low density cholesterol and triglycerides) • Pregnancy testing for women of child bearing potential (WOCBP)**
Inclusion/exclusion criteria reviewed	
Complete physical exam	
Clinician assessments (Lesion count, Hurley stage, HASI)	
Clinical photography of all lesions (do not include face)- kept in research files	
ECG	
Alcohol intake and recreational drug use	
Begin weekly surveys (more details below)	

*All blood will be obtained at Penn State Health outpatient laboratory.

**If subjects are postmenopausal, (defined as amenorrhea at least 12 months before screening) this will be confirmed by FSH levels drawn at the clinical site (approx. 2 teaspoons of blood)

Begin weekly surveys – These will be completed by the participants weekly through the end of Week 16 through REDCap. The weekly instruments will include patient-reported measures: NRS pain with 24-hour recall, NRS pain with 7-day recall, Hidradenitis suppurativa Quality of Life instrument (HiSQOL); medication use (assessing use of rescue medications or other potentially modifying medications or interventions).

7.2.2 Week 0, Baseline visit (28 ±5 days)- Can be combined with Screening Visit

Subjects will have a combined Screening/Baseline visit if all Inclusion/Exclusion criteria is met at the Screening visit.

Complete physical exam	Patient reported measures- collected electronically
------------------------	---

Clinician reported measures collected	WOCBP only- urine sample for pregnancy
Clinical photography	Dispense and start treatment with topical ruxolitinib 1.5% cream. Study coordinator will provide instructions for twice daily application.
Target lesion evaluated	Tissue sample collected (details below)

Tissue sample of Target Lesion: We will collect a full-thickness skin punch biopsy (4-6mm) from an active inflammatory lesion from each subject as a mandatory part of the study. Gelfoam will be immediately applied to the area after the biopsy procedure. Vaseline will be placed where the biopsy was taken to help the healing process. We are collecting lesional HS skin only. One punch biopsy will be collected at Week 0 of the target lesion/area.

For all full-thickness skin punch biopsies, skin punch will be immediately placed in sterile specimen cup and transported on ice to [name] laboratory (C7801 BMR) for storage and analysis. Biopsy will be bisected and portions will be formalin-fixed paraffin-embedded for planned immunohistochemistry analyses. Remaining biopsy portion will be placed in RNALater and stored at -80C. Total RNA will be isolated from the skin punch and may be subjected to RNA-sequencing in future studies.

7.2.3 Week 4 (± 5 days)

Clinical photography	Target lesion evaluated
Patient reported measures- collected electronically	All used/ unused study medication returned
Clinician reported measures	New study medication dispensed
Complete physical exam	WOCBP only- urine sample for pregnancy

7.2.4 Week 8 (± 5 days)

Clinical photography	Target lesion evaluated
Patient reported measures- collected electronically	All used/ unused study medication returned
Clinician reported measures	New study medication dispensed
Complete physical exam	WOCBP only- urine sample for pregnancy

7.2.5 Week 16/Early Termination (± 5 days)

Clinical photography	Laboratory Testing (approx. 8 tsp blood):
Complete physical exam	
 • CBC with differential • Hepatic panel (AST, ALT, Alk phos) • Fasting lipid panel (Total, high-density, and low density cholesterol, and triglycerides) • WOCBP only- urine sample for pregnancy
Patient reported measures-completed electronically	
Clinician reported measures	
Tissue sample collected (details below)	
Target lesion evaluated	
All dispensed medication (used and unused) will be returned to the research office	

Tissue sample of Target lesion identified at the baseline visit (whether active or resolved): We will collect a full-thickness skin punch biopsy (4-6mm) from the target lesion.

For all full-thickness skin punch biopsies, skin punch will be immediately placed in sterile specimen cup and transported on ice to [name] laboratory (C7801 BMR) for storage and analysis.

Biopsy will be bisected and portions will be formalin-fixed paraffin-embedded for planned immunohistochemistry analyses.

Remaining biopsy portion will be placed in RNALater and stored at -80C. Total RNA will be isolated from the skin punch and may be subjected to RNA-sequencing in future studies.

7.2.6 F/U Telephone Call (30 days post last dose of study medication) (+7 days)

Coordinator will call participant and discuss any new A/E's or changes in medication since the last dose of study medication.

7.3 Duration of Participation

During the study, participants will have scheduled visits in the Dermatology Research Office at Screening, Baseline/Week 0 (can be combined with Screening), Week 4, Week 8, and Week 16. Each of these visits is expected to last for up to 60 minutes.

Participation will be up to 24 weeks long, including the screening and follow up periods.

7.4 Test Article(s) (Study Drug(s) and/or Study Device(s))

7.4.1 Description

Topical ruxolitinib 1.5% cream is an investigational treatment for hidradenitis suppurativa. The drug molecule, ruxolitinib, is FDA-approved to treat myelofibrosis and polycythemia vera. Ruxolitinib inhibits janus-associated kinases (JAK) 1 and 2. Which leads to disruption of cytokine and growth factor signaling pathways. Topical ruxolitinib 1.5% cream is not FDA-approved for any

indication, so an IND will be obtained from the FDA for use. The cream will be supplied by the company, Incyte.

7.4.2 Treatment Regimen

A thin layer of Topical ruxolitinib 1.5% cream will be applied to areas of hidradenitis suppurativa on the skin twice a day.

7.4.3 Method for Assigning Subject to Treatment Groups

NA

7.4.4 Subject Compliance Monitoring

Tubes of the study medication will be weighed at every study visit. Study team will re-educate subjects for dosing administration at all study visits.

7.4.5 Blinding of the Test Article

NA

7.4.6 Receiving, Storage, Dispensing and Return

7.4.6.1 Receipt of Test Article

Tubes of ruxolitinib 1.5% cream will be obtained from Incyte, the sponsor. The IP will each be dispensed in 60g tubes. Labeling will include instructions that the product is for external use only, to use the IP twice daily on the skin at sites of HS.

7.4.6.2 Storage

The IP cream can be stored at ambient temperature (15°C-30°C/59°F-86°F). IP will be stored in our Investigational Drug Services Pharmacy. Temperatures will be monitored and recorded by the SensoScientific Temperature monitoring system.

7.4.6.3 Preparation and Dispensing

Topical ruxolitinib 1.5% cream will be provided by Incyte, so no preparation is needed. The amount of tubes dispensed to each participant depends on their lesion count. The investigator (or designee) is responsible for study treatment accountability, reconciliation, and record maintenance (i.e., receipt, reconciliation, and final disposition records). Inventory and accountability records will be maintained and readily available for inspection by the study monitor and are open to inspection at any time.

by any applicable regulatory authorities. The participant will administer the topical cream after teaching by the investigator (or designee).

The investigator or designee will maintain records that document:

- Delivery of study drug to the study site.
- Inventory of study drug at the site.
- Participant use of the study drug including tube weights from each supply dispensed.
- Return of study drug to the investigator or designee by participants.

The investigational product will be used only in accordance with the Protocol. The investigator will also maintain records adequately documenting that the participants were provided the specified study drug, including the dates, quantities, and any available batch or serial numbers or unique code numbers assigned to the investigational product and study participants. All IP will be maintained by Investigational Drug Service.

7.4.6.4 Return or Destruction of the Test Article

The investigator (or designee) will be expected to collect and document all used, unused, and partially used containers of study drug dispensed to subjects. Once the returns have been accounted for by 2 members of the IDS pharmacy team, the medications will be destroyed as per the Investigational Drug Service Destruction Policy. Expired study medications will be destroyed as per the Drug Services Pharmacy Policies. At the conclusion of the study, any remaining study drug will be destroyed as per the Investigational Pharmacy Policies. Accountability records documenting the destruction will be available for review by the study monitor.

7.4.6.5 Prior and Concomitant Therapy

All concomitant medications and treatments (including over-the-counter or prescription medicines, vitamins, vaccines, and/or herbal supplements) will be recorded on electronic study forms in REDCap. Any addition, deletion, or change in the dose of these medications will also be recorded. Concomitant treatments/procedures that are required to manage a participant's medical condition during the study will also be recorded in the REDCap study forms.

Any prior medication received up to 28 days before the first dose of study treatment and 30 days after the last dose of

study treatment will be recorded in the REDCap study forms. A detailed history of prior medications use related to HS in the year before screening will be also be collected, as well as response to each treatment and reason for discontinuation.

Excluded/prohibited concomitant medication and procedures include: JAK inhibitors (systemic or topical (eg, ruxolitinib, tofacitinib, baricitinib, filgotinib, lestaurtinib, and pacritinib)) in the 4 weeks prior to screening; surgical, laser, or IPL intervention in area with HS lesion in prior 3 months and except for rescue lesional treatment (see below); topical use of creams, ointments, gels, and liquids except the study therapy.

All medications used by the patient will be reconciled at entry into the study and through electronic surveys or in-person study visits throughout the entire study duration.

If a participant experiences significant pain after baseline, one of the following analgesic regimens may be initiated at any time: Ibuprofen (at a dose of up to 800 mg orally every 6 hours) not to exceed 3200 mg/24 hours OR acetaminophen not to exceed 4 g/24 hours. Participants can use one of the permitted antiseptic therapies. Permitted antiseptic washes are limited to one of the following: chlorhexidine gluconate, triclosan, benzoyl peroxide, or diluted bleach in bathwater. Participants can use wound care dressings on HS wounds. Options are limited to alginates, hydrocolloids, and hydrogels.

In the event of an acutely painful lesion that requires immediate intervention, the investigator and participant will have the option to perform protocol-allowed interventions. Two types of interventions are permitted: injection with intralesional triamcinolone acetonide suspension (up to 40 mg in total at the same visit) and/or incision and drainage. New systemic and topical therapies following incision and drainage, including antibiotics, are prohibited. Participants should continue using the topical study therapy. From Day 1 through Week 16, an intervention can occur on a maximum of 2 different lesions at the same visit or on the same lesion at 2 different study visits. The same lesion cannot be treated 2 times during the same visit. If participants require more than 3 interventions before Week 16, then the study drug will be discontinued for those participants. Study procedures must be performed before any interventions. Any lesion undergoing an intervention will be documented in the lesion count worksheet.

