1.2 Primary Study Endpoints

The primary efficacy measure is the proportion of participants that achieve HiSCR (is the total number of abscess and inflammatory count of the participants lesions) at Week 16 with topical ruxolitinib 1.5% cream as compared to Baseline (Week 0). The HiSCR is defined as at least a 50% reduction in the total abscess and inflammatory nodule count (AN count) for all study body sites with no increase in abscess count and no increase in draining fistula count relative to Baseline. The primary efficacy analysis will be carried out on all participants who complete 16 weeks of treatment.

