1.3 Secondary Study Endpoints

- Mean difference in the International Hidradenitis Suppurativa Severity Scoring System (IHS4) score from Baseline to Week 16.
- Proportion of patients who are clear or mild by IHS4 after 16 weeks of treatment.
- Mean difference in the novel clinician-reported outcome measure (HASI, investigator-supplied) score from Baseline to Week 16.
- Mean change in the Hidradenitis Suppurativa Quality Of Life (HiSQOL) instrument for 16 weeks of treatment.
- Mean change in Numerical Rating Scale (NRS) for pain (7-day) after 16 weeks of treatment.
- Proportion of participants with a 30% and at least 2-point reduction in NRS for pain (7-day) after 16 weeks of treatment.
- Mean change in Numerical Rating Scale (NRS) for pain (24-hour) after 16 weeks of treatment.
- Proportion of participants with a 30% and at least 2-point reduction in NRS for pain (24-hour) after 16 weeks of treatment.

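### The four secondary pain endpoints are scored without regard to rescue analgesics or lesion interventions, and the planned report does not show how often rescue precedes a lower Week 16 score

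*Combined protocol and SAP*

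**What the plan says.** **Endpoints.** Section 1.3 lists four pain endpoints: a mean change and a responder rate, each with 7-day and with 24-hour recall. The responder endpoint (NRS30 below) reads, for the shorter recall, "Proportion of participants with a 30% and at least 2-point reduction in NRS for pain (24-hour) after 16 weeks of treatment"; the 7-day version uses the same criterion. None of the four mentions rescue.

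**Permitted rescue.** Section 7.4.6.5 states: "If a participant experiences significant pain after baseline, one of the following analgesic regimens may be initiated at any time". The choices are ibuprofen up to 3200 mg or acetaminophen up to 4 g in 24 hours. On lesions it states: "In the event of an acutely painful lesion that requires immediate intervention, the investigator and participant will have the option to perform protocol-allowed interventions". These are triamcinolone injection, incision and drainage, or both. Two limits apply to lesion interventions. One is the order of events at a visit: "Study procedures must be performed before any interventions". The other is that study drug stops if more than 3 interventions are needed before Week 16.

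**Records.** The weekly REDCap survey (Section 7.2.1) covers "medication use (assessing use of rescue medications or other potentially modifying medications or interventions". For concomitant medication, Section 7.4.6.5 adds: "Any addition, deletion, or change in the dose of these medications will also be recorded". Treated lesions are entered on the lesion count worksheet.

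**Analysis.** Section 8.3 does not name NRS pain in its list of secondary endpoints. It says that secondary variables are summarised in the ITT population, which it defines as those who complete the study. Its only data-handling rule is last observation carried forward (LOCF) for missing data.

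**The concern.** The trigger for rescue is pain, and pain is what these four endpoints measure. Someone whose Week 16 score is low while taking ibuprofen, or after a painful lesion was drained, counts in the same way as someone who improved on the cream alone. The trial is open label with one cohort (Sections 3.1 and 8.2), and assignment and blinding are marked not applicable (Sections 7.4.3 and 7.4.5). No comparison arm with the same access to rescue exists to show what rescue contributes.

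At stake is how the pain results can be read. They are four of the eight secondary endpoints in Section 1.3, and readers are likely to take them as evidence on pain relief. As planned, a reader could not tell whether none or many of the pain responders had rescue. If the rule is chosen after the scores are known, the choice could also be influenced by them.

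**Working it through.** The plan gives no sample size, power or expected effect for the pain endpoints, so there is no stated figure to reproduce. The check asks whether any existing rule deals with scores taken on or after rescue, and then what one participant is worth.

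1. **Endpoint definitions (Section 1.3).** They compare Week 16 with Baseline and set no condition on rescue.

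2. **LOCF (Section 8.3).** It applies to missing scores. A score recorded while on an analgesic is not missing, so LOCF leaves it as it stands.

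3. **Order within a visit (Section 7.4.6.5).** This protects the scores taken at that visit. It does not limit oral analgesics, which may start at any time, and it does not cover later scores. Section 7.3 gives the visits as "Baseline/Week 0 (can be combined with Screening), Week 4, Week 8, and Week 16". Sections 7.2.3 to 7.2.5 allow 5 days either way at each post-Baseline visit.
   - Week 8 to Week 16: 8 × 7 = 56 days; range 56 − 10 = 46 to 56 + 10 = 66 days.
   - Week 4 to Week 16: 12 × 7 = 84 days; range 84 − 10 = 74 to 84 + 10 = 94 days.

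   A 7-day look-back from Week 16 would therefore miss interventions at both visits. A rule for lesion rescue has to run from the Baseline score to the Week 16 score. This does not show that an intervention still affects pain at Week 16; the documents do not say.

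4. **Stopping drug after more than 3 interventions (Section 7.4.6.5).** This is a treatment rule and does not say how the scores count. Such participants may drop out of the analysed set, because Section 1.2 analyses those who complete 16 weeks of treatment and Section 8.3 those who complete the study. Participants with one to three interventions, or with analgesics only, stay in.

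5. **Use of the rescue records.** The survey, the REDCap medication forms and the lesion worksheet collect rescue. No planned efficacy analysis refers to them.

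6. **Size.** Input: n = 18 completers (Section 8.1). Let k be the number recorded as NRS30 responders who also meet a rescue rule. The as-recorded rate minus the rate counting them as non-responders is k / n. For k = 1 this is 1/18 = 0.056, or 5.6 percentage points. The documents give no value for k, no rescue rate and no pain standard deviation, so the total gap and any shift in the means cannot be calculated.

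**The case against.** The strongest reply is that the trigger works against inflation. Rescue begins when pain is significant after Baseline, whereas an NRS30 responder must be at least 30% and 2 points below Baseline. Treating a flare may only return the score towards Baseline, which earns no response. Participants already taking analgesics at Baseline may cut down, which would hide benefit. The heaviest users of lesion rescue stop study drug and may leave the completer set. All of this stands, and it means that no direction can be claimed. It does not rule out the case where a lesion already painful at Baseline is drained, or where analgesics bring the score below the threshold.

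It can also be said that these endpoints are secondary and only summarised, that including permitted rescue is a recognisable approach, and that stable biologics or antibiotics and permitted antiseptic washes are not separated from the cream either. That supports keeping the as-recorded results. It is no reason to leave rescue out of the report when it is collected.

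Two practical objections hold in part. An increase in as-needed use by someone already on analgesics at Baseline may not be captured, since the protocol mentions medication use and dose changes but not frequency. And counting one early intervention as non-response at Week 16 is strict. Both are reasons to label the second rate as a sensitivity result.

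**Conclusion.** The point holds for the four secondary pain endpoints. The plan permits rescue for pain, scores pain without regard to it, and plans no display of how often it occurred. With 18 completers, each reclassified participant moves an NRS30 rate by 5.6 points. That is the only magnitude the documents support, and it assumes exactly 18 in the denominator.

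A reader might infer that the reported pain response is inflated, or that relief from rescue is a large part of it. The documents support neither, because the net direction and size depend on who takes rescue and why, and nothing in the protocol settles that. A reader might also infer that the primary result is compromised by analgesics. Analgesic use does not enter the definition of HiSCR. Lesion interventions are different: they can change the lesion count, on which a HiSCR responder needs "at least a 50% reduction in the total abscess and inflammatory nodule count (AN count) for all study body sites". That needs its own rule and is not covered here.

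The change should be made before the data are analysed. It affects how the pain results are read and does not alter the conduct of the trial.

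**What to change.** Add a short paragraph to Section 8.3:

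1. **Tabulate rescue.** Give the number of participants with any analgesic use in the 7 days before the Week 16 score, and the number with any lesion intervention permitted by Section 7.4.6.5 after the Baseline score.
2. **Two NRS30 rates for each recall period.** Keep the rate as recorded. Beside it, report a sensitivity rate that counts as non-responders those who, in the 7 days before the Week 16 score, used an analgesic newly started after Baseline or with a recorded dose increase, and those who had a permitted lesion intervention between the Baseline and Week 16 scores. If LOCF supplies the score, use the date of the carried score in place of Week 16. Label this rate conservative, and state that it is not a bound on the true rate.
3. **Mean changes.** Report each as recorded, with the rescue count beside it. Do not present a mean that excludes rescue users as a corrected estimate: it selects participants who are doing better and could look more favourable.

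Leave the permitted rescue unchanged.

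The cost is one extra rate for each of the two responder endpoints and a small table, drawn from the weekly survey, the REDCap medication records and the lesion worksheet. The downside is a possibly lower pain response rate and some over-penalising, for example of an analgesic taken for headache (which Section 10.0 allows) or of an early lesion intervention. The as-recorded rate beside it keeps this visible.

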3.0 Inclusion and Exclusion Criteria

3.1 Inclusion Criteria

1. Male or female subjects age 12 years or older
 - This inclusion criteria has been updated due to the approval of the study medication for use in this age group (12 years and older) in other indications. Additionally, Humira, an approved biologic medication for HS, is also used in this population, highlighting the need for topical breakthrough treatments for those affected by HS at younger ages. Due to the open-label nature of this medication and the anticipated benefits for any children participating, the greater than minimal risk of this study design is justified.
2. Hidradenitis suppurativa, and should be Hurley Stage I or II, defined as papules, nodules, and/or abscess formation, single or multiple, with or without sinus tracts;
3. Subjects must have a diagnosis of HS for at least 3 months (90 days) prior to Baseline;
4. Active HS lesions must be present in at least one distinct anatomic area;

5. Subject must have at least 3 total inflammatory lesions at the Baseline visit;
6. Subjects who had surgery in the treatment area, should be at least 3 months status post the procedure (this applies to deroofting/marsupialization or excision, not incision & drainage)
7. Subject has a negative TB screening assessment (including a PPD test and/or T-Spot) OR for patients with treated latent TB or negative chest x-ray (CXR posterior-anterior [PA] and lateral view within prior 90 days) at Screening with documentation of treated latent tuberculosis (90 days of treatment).
8. Medications can be continued if they have been at a stable dose for the requisite duration and the dose is not increased during the study period:
 - Biologic medication (such as TNF α , IL-12/23 or IL-17 inhibitors): Up to 30% of enrolled participants will be allowed to remain on a concurrent biologic at stable dosage if treated with a stable dose and frequency for 6 months or longer;
 - Oral antibiotic must be a stable dose and frequency for 28 days or longer;
 - Hormone-based therapy (birth control pills or spironolactone) must be a stable dose and frequency for 4 months or longer;
 - Oral retinoids must be on a stable dose and frequency for 90 days or longer;
 - Other topical therapy must be discontinued 14 days prior to the Baseline visit.

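### Section 7.4.6.5 sets the same rescue-analgesic ceilings for a 12-year-old as for an adult, with no adjustment for age or weight

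*Combined protocol and SAP*

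**What the plan says.** **Who may enter.** Inclusion criterion 1 in section 3.1 reads "Male or female subjects age 12 years or older". The note beneath it explains: "This inclusion criteria has been updated due to the approval of the study medication for use in this age group". It adds that another hidradenitis treatment is used at that age. Sections 3.1 and 3.2 set no minimum body weight. Minors are clearly planned for. Section 5.6.3.1 states "For all subjects under the age of 18, parental/legal guardian permission will be obtained using an informed consent form", and section 5.6.3.2 provides for assent at ages 12 to 17.

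**What rescue analgesia is allowed.** Section 7.4.6.5 says that, for a participant in significant pain, "one of the following analgesic regimens may be initiated at any time". The first option is "Ibuprofen (at a dose of up to 800 mg orally every 6 hours", and the daily limits are "not to exceed 3200 mg/24 hours OR acetaminophen not to exceed 4 g/24 hours". The two drugs are alternatives and the figures are maxima. The section gives no age or weight condition, no limit on duration, and no single dose or interval for acetaminophen. It does not say who starts or directs the analgesic. The later text on injecting or draining a painful lesion, by contrast, names the investigator and the participant.

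**How use is tracked.** Section 7.4.6.5 says "All medications used by the patient will be reconciled at entry into the study and through electronic surveys or in-person study visits". The weekly survey in section 7.2.1 covers "medication use (assessing use of rescue medications or other potentially modifying medications or interventions".

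**The concern.** A protocol ceiling defines the most that a participant may take without departing from the plan. Here that bound is identical for a light 12-year-old and a full-grown adult. The reasons given for admitting 12-year-olds concern the study cream and another hidradenitis drug, and neither bears on oral ibuprofen or acetaminophen. The risk table in section 10.0 has no entry on analgesic dosing in minors.

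The other safeguards act at entry or after use. Parental permission and the investigator's judgement of suitability govern who joins. Surveys, medication reconciliation, physical examinations, adverse-event monitoring and ongoing safety review detect use or harm once it has occurred. The hepatic panel is scheduled only at Screening and at Week 16 or early termination. None of these sets a lower limit for a minor beforehand.

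What is at stake is the safety of children in a study whose risk to them the protocol itself describes as more than minimal. The primary endpoint, sample size and analysis are not involved.

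**Working it through.** **Inputs from section 7.4.6.5:** ibuprofen single dose 800 mg, interval 6 h, daily ceiling 3200 mg; acetaminophen daily ceiling 4 g = 4000 mg.

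**Assumed input:** body weight. The documents give no participant weights, so a range is shown, with 70 kg as the reference for an adult.

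**Step 1: reproduce the plan's figure.** Doses per day = 24 / 6 = 4, and 4 × 800 mg = 3200 mg. The ibuprofen ceiling agrees with its own dose and interval, so taking the written regimen in full reaches the daily maximum.

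**Step 2: ceiling per kilogram.** Per-kg ceiling = fixed ceiling / weight. Ratio to the 70 kg reference = 70 / weight.

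| Assumed weight (kg) | Ibuprofen, mg/kg/day (3200 / weight) | Acetaminophen, mg/kg/day (4000 / weight) | Ibuprofen single dose, mg/kg (800 / weight) | Ratio to 70 kg |
|---|---|---|---|---|
| 40 | 80.0 | 100.0 | 20.0 | 1.75 |
| 50 | 64.0 | 80.0 | 16.0 | 1.40 |
| 60 | 53.3 | 66.7 | 13.3 | 1.17 |
| 70 | 45.7 | 57.1 | 11.4 | 1.00 |

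The ibuprofen and acetaminophen columns are alternatives and are not to be added. No single-dose column is possible for acetaminophen, because the section gives only a daily total.

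**Step 3: look for a limit to compare with.** No section states a paediatric maximum for either drug. The table therefore shows how a fixed ceiling scales with weight. It does not show an excess over any limit.

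**Step 4: look for a count of those affected.** Section 8.1 anticipates about 24 people and at least 18 completers, with no breakdown by age. The number of minors cannot be derived and could be zero.

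**The case against.** The best reply is that no harm is demonstrated. Without a paediatric limit in the documents, the table says only that a fixed amount divided by a smaller weight is a larger number. The wording is permissive and sets upper bounds, so nobody is told to take the maximum. Section 10.0 allows analgesics for headache only where suitable, which presumes clinical judgement. Complete physical examinations take place at every visit, abnormal screening laboratory results can exclude a participant, and a parent or guardian is involved. The Information Sheet for ages 12 to 17 and the consent form are not available for review and may already carry dosing advice. Finally, the exposure argument concerns weight while a split at age 18 concerns age, so a 40 kg adult would keep the same per-kg ceiling.

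Most of this stands, and it limits the severity. It does not remove the point: section 7.4.6.5 is an explicit rule, and it permits the adult maximum at any eligible age and weight. The age split is imperfect, but 18 is where the protocol already changes its consent procedure, and an investigator may set the present ceiling for a minor of adult weight.

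Three stronger readings are tempting, and the documents support none of them:

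- *The ceilings are an overdose for a 12-year-old.* This needs a paediatric limit that the documents do not give.
- *An adult-only rule was left behind when the age limit was lowered.* Section 3.1 says that the criterion was updated but not from what age, and nothing dates the analgesic text.
- *Minors will dose themselves without oversight.* Section 7.4.6.5 leaves the decision-maker unstated, which does not show that clinical or parental judgement is absent.

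**Conclusion.** The point holds as a low-severity safety improvement. The plan enrols from age 12 with no minimum weight and applies one fixed set of analgesic ceilings to everyone, so the full adult amount is protocol-compliant for a light minor.

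The only size that can be given is relative. The per-kg ceiling is 1.75 times the 70 kg value at 40 kg, 1.4 times at 50 kg and 1.17 times at 60 kg, all at assumed weights. A minor who weighs as much as an adult is unaffected. By how much, if at all, the ceilings exceed a suitable paediatric maximum cannot be stated from these documents. Nor can the number of minors exposed, or whether participant-facing material already gives dose advice.

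**What to change.** Amend section 7.4.6.5 in two respects:

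- State that the present ibuprofen and acetaminophen ceilings apply to participants aged 18 or older.
- State that, for ages 12 to 17, the single dose, the interval and the 24-hour total must not exceed the age- and weight-appropriate maximum, which the investigator sets and tells the participant and the parent or guardian at Baseline.

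No specific paediatric dose is proposed here, because the documents provide no basis for one. The evidence does not call for an individual written analgesic plan, a contact before each rescue dose, or a pause in enrolling minors. Giving the maximum in advance means that pain relief is not delayed.

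The cost is a short protocol amendment, plus one body weight and a brief instruction per minor at a visit that already includes a complete physical examination. The documents do not itemise that examination, so weight may already be measured. If the Information Sheet or consent form mentions analgesic doses, it should be brought into line. Sample size and analysis are unchanged.
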